### **Categorical Data.**

The following categorical data will be analyzed in the study:

Safety:

- Rate and severity grades of AEs/SAEs
- Rate of Grade 3-4 AEs,
- Incidence of administration site reactions.
- Frequency of local reactions (total and by skin disorder type).
- Frequency of early withdrawals due to AEs.

Categorical data will be processed using frequency tables, contingency tables, the Fisher's exact test, the test of equal frequencies, Pearson's  $\chi^2$  test, and the Cochran-Mantel-Haenszel test. Percentages or proportions will be used to describe categorical data. The Benjamini-Yekutieli correction for multiple testing will be used. Statistical methods will be chosen according to the

type of initial data and their distribution. Appropriate statistical tests will be established after the data collection has been completed because the type of data distribution, sample homogeneity, etc. are unknown before the study start. For appropriate data processing, the list of statistical methods used may expand during the analysis.

Descriptive statistics for the data on drug concentration in the serum, effect values, and protocol-specified PK and PD parameters will be performed using the following: mean values, geometric mean values, standard deviations, medians, upper and lower quartiles, min and max, and the coefficient of variation.

The statistical comparison involves the calculation of two-sided parametric 90% confidence intervals (CIs) for the ratios of the  $AUEC_{(1-29)}$  means for hemoglobin and darbepoetin alfa following the IV injection of BCD-066 and Aranesp®, and comparison of these CIs with the PD equivalence interval:  $AUEC_{(1-29)}$  80-125%.

The study drugs will be considered equivalent if the estimated 90% CIs for the mean  $AUEC_{(1-29)}$  ratio for darbepoetin in BCD-066 and darbepoetin in Aranesp® will fall in the said range.

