	
 – The elimination half-life ($T_{1/2}$) – The total area under the Concentration vs. Time curve from 0 to infinity (AUC_{0-168}) – The time to maximum drug concentration in the serum (T_{max}) – The residual area – The elimination constant (k_{el}) – The total clearance (CL). 
Methods used for PK assessment: The PK analysis will include all subjects who have received all doses of the test/reference drug as per protocol. Not more than 2 PK blood collections after the first injection and not more than 2 PK blood collections after the fourth injection can be missed. Subjects who have two consecutive blood samples missed will be not included in the analysis. The PK parameters will be analyzed based on darbepoetin alfa concentrations in the subject’s serum.

PD Endpoints
	
Endpoints:
 
 • Primary endpoint: 
 — The area under the baseline-adjusted Effect vs. Time curve from injection to Day 29 after the repeated-dose IV administration of the test/reference drug ($AUEC_{(1-29)}$). • Secondary endpoints: 
 — The maximum increase in hemoglobin from baseline, estimated from injection to Day 29 after the repeated-dose IV administration of the test/reference drug ($AC-E_{max}$). 
Supplementary endpoints:
 
 — The time to the absolute maximum increase in hemoglobin from injection to Day 29 after the repeated-dose IV administration of the test/reference drug (T_{max}). 
In addition, PD parameters ($AUEC$, $AC-E_{max}$, and T_{max}) will be estimated based on the reticulocyte and RBC counts and on hematocrit values.
 
Methods used for pharmacodynamic assessment:

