### **3.3. Selection of Study Population**

#### **1.3.1. Inclusion criteria**

1. Signed informed consent form
2. Men from 18 to 45 years old (inclusive)
3. BMI within the normal limits (18.5 to 30 kg/m^2)
4. Hemoglobin from 120 g/L to 150 g/L and hematocrit 41% to 49% at screening (before the first injection)
5. Serum transferrin 2.15 g/L to 3.6 g/L; serum ferritin from 20 µg/L to 250 µg/L
6. Vitamin B12 from 187 pcg/mL to 883 pcg/mL; folic acid from 3.1 ng/mL to 20.5 ng/mL
7. Endogenous serum erythropoietin < 30 mIU/mL at screening
8. The subject is verified as “Healthy” according to results of standard clinical, laboratory and instrumental tests
9. Subject’s ability (in the investigator’s opinion) to follow the protocol procedures

10. The subject and his sexual partner with retained childbearing potential consent to implement reliable contraceptive methods starting 2 weeks before inclusion in the study and up to 2 weeks after the last dose of the test/reference drug. This requirement does not apply to surgically sterile subjects. Reliable contraception methods mean one barrier method in combination with one of the following: spermicides, intrauterine device and/or oral contraceptives used by the subject's partner.
11. The subject agrees not to drink alcohol for 24 h prior to each injection of the test/reference drug and for 72 h after the injection.

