#### **4.2. Pharmacodynamics Endpoints**

- Primary endpoint:  
AUEC(1-29) (the area under effect curve) based on the change of hemoglobin level from the moment of injection to Day 29 after the repeated IV administration of the test/reference drug
- Secondary endpoints:  
AC- $E_{max}$  (the maximum increase in hemoglobin level from baseline), from the first injection to Day 29 after the repeated IV administration of the test/reference drug
- Supplementary endpoints:  
 $T_{max}$  (the time to the absolute maximum increase of hemoglobin level from injection to Day 29 after the repeated IV administration of the test/reference drug).  
In addition, PD parameters (AUEC, AC- $E_{max}$  and  $T_{max}$ ) will be estimated based on the reticulocyte and RBC counts and on hematocrit values.

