#### **6. SAMPLE SIZE CALCULATION**

The sample size was determined using the variation coefficients for hemoglobin increase (Hb AUEC) obtained by Cheung, 2001. The estimated Type I error was 5% ( $\alpha=0.05$ ) and Type II error was 20% ( $\beta=0.2$ ), with the test power of 80%.

The sample size was calculated with the “sample N.TOST” function of the “PowerTOST” package for R. The calculation used the CV values and the ratios of the mean Hb increases (AUEC).

$$CV_{AUC(Hb)}(\%) = \frac{\sigma_{AUC(Hb)}}{\bar{x}_{AUC(Hb)}} = \frac{12.92}{45.4} = 28.46\%$$

**Table 1.** Test power and sample size

Index	Mean value ratio	CV (%)	Sample size (N)	Test power
AUEC (1-29) hemoglobin	$\frac{\mu_T}{\mu_C} = 1$	28,46	N AUC(Hb)} = 56 volunteers. (28 volunteers per group)	80,95%

The study should include 28 subjects per group and 6 subjects as backups to replace potential early withdrawals (62 volunteers total).

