3.  $AUEC_{(1-29)}$  – area under effect curve from the moment of injection to the day 29 after repeated IV injections test drug/reference drug based on the hemoglobin level (reticulocytes counts, RBC, hematocrit)

$AUEC_{(1-29)}$  will be calculated as:

CONFIDENTIAL

Version 1.0 dated 10-Oct-2016

Page 16 of 17

$$AUEC_{(1-29)} = \sum_{p=2}^{16} \frac{(C_p + C_{p-1}) * (t_p - t_{p-1})}{2},$$

где  $C_p$  hemoglobin level (reticulocytes counts, RBC, hematocrit) in the time point  $t_p$  (days);

$$t_p \in \{ 0; 1; 3; 5; 7; 8; 10; 12; 14; 15; 17; 19; 21; 22; 24; 28 \}; p=1, \dots, 16$$

4. **AC-Emax** – absolute maximum increase in the test parameter vs. baseline based on the change in the hemoglobin level (absolute reticulocyte count, erythrocytes count)

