### **8.7. Subgroup analysis, interaction and related variables**

Not available.

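### The SAP 8.4 formula for the primary AUEC(1-29) integrates raw hemoglobin, not the baseline-adjusted change, so a much weaker product could pass 80-125%; a Day 1 hemoglobin covariate is an optional extra once this is corrected

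*SAP*

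**What the plan says.** Three places describe the primary pharmacodynamic area net of baseline:

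- Protocol, PD Endpoints: "The area under the baseline-adjusted" effect-time curve, from injection to Day 29.
- SAP 4.2: an area "based on the change of hemoglobin level from the moment of injection to Day 29".
- SAP 6: the sample size rests on "variation coefficients for hemoglobin increase (Hb AUEC"), with CV 12.92/45.4 = 28.46%, a true ratio of 1, 28 subjects per group and 80.95% power.

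The computing instruction in SAP 8.4 differs. It defines the area "after repeated IV injections test drug/reference drug based on the hemoglobin level" and applies the trapezoid rule to C_p, which it defines as the hemoglobin level at each time. The time grid in days is "0; 1; 3; 5; 7; 8; 10; 12; 14; 15; 17; 19; 21; 22; 24; 28". Its first point, t = 0, is the Day 1 pre-dose sample, but that value is not subtracted from the later ones. The list of quantitative data in SAP 8.2 also describes the curve as hemoglobin level against time.

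The primary comparison in SAP 8.2 is "The statistical comparison involves the calculation of two-sided parametric 90% confidence intervals (CIs) for the ratios of the" AUEC(1-29) means. No model, scale or covariate is named. SAP 8.7, headed "Subgroup analysis, interaction and related variables", offers nothing. SAP 10 states that there are no departures from the protocol's methods.

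**The concern.** A programmer who follows SAP 8.4 literally will compute a different variable from the protocol's primary endpoint. Most of a raw hemoglobin area is the hemoglobin that the volunteer had before dosing, which is the same in expectation in both randomized groups. This shared component pulls the ratio of the two group means towards 1. Limits of 80-125% are then very wide relative to any difference in drug effect, and the trial loses its ability to detect a weaker product. The SAP 6 power calculation would no longer describe the test performed.

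A smaller question follows. Subtracting baseline need not remove all dependence of the hemoglobin rise on baseline. Every subject has a scheduled Day 1 pre-dose value, so a covariate might add precision at no cost in data.

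**Working it through.** **1. Reproducing the plan's figure.** Inputs from SAP 6 and 8.2: CV 28.46%, 28 per group, ratio 1, limits 0.80-1.25, two one-sided tests at 0.05 each (the 90% CI).

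- Log-scale variance: ln(1 + 0.2846²) = 0.0779, so SD = 0.279.
- SE = 0.279 × √(2/28) = 0.0746, with 54 df.
- Exact power = 80.95%, as stated. At a true ratio of 0.95 it is 71.2%.
- On the untransformed scale, 56 subjects give 77.5% and 60 would be needed.

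The planned power therefore presupposes a log-scale analysis, although SAP 8.2 does not say so.

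**2. The raw area.** Assumptions, not in the documents: baseline 135 g/L (the midpoint of the 120-150 g/L eligibility range) and a time-averaged reference rise m of 5, 10 or 15 g/L. The 28 days cancel, so:

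- half the effect: ratio = (135 + m/2)/(135 + m)
- no effect: ratio = 135/(135 + m)

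| m (g/L) | Half the effect | No effect |
|---|---|---|
| 5 | 137.5/140 = 0.982 | 135/140 = 0.964 |
| 10 | 140/145 = 0.966 | 135/145 = 0.931 |
| 15 | 142.5/150 = 0.950 | 135/150 = 0.900 |

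The CV of the raw area is also undocumented; 5-15% is assumed. For orientation, hemoglobin spread evenly over 120-150 g/L has SD 30/√12 = 8.66 g/L, a CV of 8.66/135 = 6.4%. The exact probability of passing with 28 per group is as follows.

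- Half the effect: lowest at m = 15 and CV 15%, where it is 99.5%; higher everywhere else in the range.
- No effect at m = 15: 99.0% at CV 11% and 89.8% at CV 15%.
- Half the effect on the baseline-adjusted area (ratio 0.50, CV 28.46%): essentially zero.

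**3. Optional covariate, on the corrected area.** Model: ANCOVA of ln(baseline-adjusted AUEC) on treatment and Day 1 pre-dose hemoglobin. Squared SE = 0.0779 × (2/28) × (1 - r²) × (1 + 1/52), with 53 df. The last factor is the expected cost of chance baseline imbalance. The correlation r is not in the documents; |r| of 0 to 0.5 is assumed.

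| \|r\| | Power, ratio 1 | Power, ratio 0.95 |
|---|---|---|
| unadjusted | 80.95% | 71.2% |
| 0 | 80.0% | 70.3% |
| 0.1 | 80.5% | 70.8% |
| 0.2 | 82.0% | 72.2% |
| 0.3 | 84.5% | 74.7% |
| 0.4 | 87.8% | 78.1% |
| 0.5 | 91.7% | 82.5% |

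Break-even is at |r| = 0.14.

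**4. Effect of eligibility.** Criterion 4 requires "Hemoglobin from 120 g/L to 150 g/L and hematocrit 41% to 49% at screening (before the first injection"). If unrestricted hemoglobin is normal with mean 145-150 and SD 10-15 g/L (assumed), truncation to 120-150 leaves k = 0.50-0.66 of the SD. With r' = rk/√(1 - r² + r²k²):

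| Unrestricted \|r\| | Restricted \|r'\| | Power, ratio 1 |
|---|---|---|
| 0 | 0 | 80.0% |
| 0.1 | 0.05-0.07 | 80.1-80.2% |
| 0.2 | 0.10-0.13 | 80.5-80.9% |
| 0.3 | 0.16-0.20 | 81.2-82.1% |
| 0.4 | 0.21-0.28 | 82.3-83.8% |
| 0.5 | 0.28-0.36 | 83.8-86.3% |

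Over the whole grid the change is about -1 to +5 points. Unrestricted |r| must exceed about 0.21-0.27 before the covariate gains anything.

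**The case against.** On the formula, the best defense is that the protocol and SAP 4.2 govern, and that SAP 8.4 only gives a generic trapezoid rule into which an analyst would put baseline-adjusted values. That intention is plausible. But SAP 8.4 defines its input expressly as the level, SAP 8.2 lists the curve the same way, and SAP 8.4 does refer to baseline when it defines AC-Emax. The ambiguity is in the primary endpoint, so it cannot be left to the analyst. The documents do not show which version would be run, so one cannot infer that a weaker product will be declared equivalent.

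On the covariate, the case against is strong and most of it stands.

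- No document requires a covariate, and the stated sample size and power reproduce without one. A reader might infer that leaving it out is an error; it is not.
- A reader might also take the 91.7% as the expected benefit. Nothing in the documents supports any particular r, and with range restriction half of the assumed grid (0, 0.1, 0.2) loses power.
- The restriction figures are themselves rough. The 120-150 g/L range applies at screening, up to 14 days before the Day 1 value, and the hematocrit limit is ignored. The true restriction could be weaker or stronger.
- A log-scale analysis needs positive areas. On the planning values, zero lies 45.4/12.92 = 3.5 SD below the mean. If areas are normal, that is 0.02% per subject and 1.2% for any of 56. Those values come from a cited study of epoetin alfa, so a rule is still needed.

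In favor of the covariate, subtracting one pre-dose value carries its random error into every time point, which tends to create a negative correlation with baseline that ANCOVA would recover. SAP 8.2 also lets methods be settled after data collection, so a decision either way should be recorded in advance.

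**Conclusion.** The SAP 8.4 formula is wrong as written: it contradicts the protocol's primary endpoint, SAP 4.2 and the basis of the sample size. On assumed rises of 5-15 g/L over 135 g/L and raw-area CVs of 5-15%, a product with half the effect would pass in at least 99.5% of trials. The exact percentages depend on those assumptions; the contradiction and the pull towards 1 do not.

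The covariate is a separate, optional improvement of uncertain sign: 80.0-91.7% power for an assumed |r| of 0 to 0.5, or about -1 to +5 points under the assumed range restriction. It does not repair the raw-area formula, because the adjusted ratio would still be a ratio of raw areas. Nor does it remove the dependence of the 80.95% on a true ratio of exactly 1.

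**What to change.** Required, in SAP 8.4 and 8.2:

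1. Replace C_p by C_p - C_1 at every time point and name C_1, the Day 1 pre-dose hemoglobin, as the baseline. Align the SAP 8.2 description of the curve, and say whether the reticulocyte, RBC and hematocrit areas are treated the same way.
2. State that the 90% CI is computed on the log scale and back-transformed before comparison with 80-125%.
3. State in advance what happens if an area is zero or negative, for example a Fieller interval for the ratio of untransformed means in all subjects.

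This costs only text. It brings the SAP back to the protocol's endpoint, and the sample size stays the same.

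Optional, before unblinding, in SAP 8.2 and 8.7: make the primary analysis an ANCOVA of ln(baseline-adjusted AUEC(1-29)) on treatment with Day 1 pre-dose hemoglobin as the only covariate, and keep the unadjusted 90% CI as a sensitivity analysis. This changes an analysis that the protocol also states, so SAP 10 must list it. It needs no new data and excludes no further subject: without a Day 1 value there is no baseline-adjusted area either, and SAP 8.3 allows no substitution. The statistical downside is about 1 point of power (79.96% against 80.95%) if r is near zero.

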### **8.3. Accounting for missing, unavailable or doubtful data, outliers**

All information specified in the e-CRFs should be supported by relevant data in source documents.

After entering all data into the electronic database, a database specialist checks it for inconsistencies, errors, and missing data points. The Clinical Study Database Manager or Medical Expert of JSC BIOCAD generates queries to correct error data or to request missing data; the queries are site-specific and subject-specific (i.e., individual queries are generated for each subject). The Clinical Study Monitor will send queries to the study site by fax or email. The queries should be resolved by the investigator within five business days from the date they have been submitted to the study site. Copies of responses to queries must be kept at the study site; original responses must be stored at JSC BIOCAD.

When responses to queries are received from investigators, the database specialist checks it for inconsistencies, errors, and missing data points. When all data at all study sites have been collected and entered, the database is closed. Afterwards, statistical processing can be started.

Missing, unused, and spurious data will not be substituted.

Spurious and unevaluable data are revealed during the outlier analysis by examination of Mahalanobis or Cook distance, visual analysis of scatter plots and box plots.

All actions taken to handle missing, unevaluable, spurious data and outliers before/during the statistical analysis will be described in the Clinical Study Report.

#### 8.4. Multivariate Comparison

Pharmacokinetic parameters

Based on determined concentrations in blood a number of the pharmacokinetic parameters will be calculated for the study drug:

1.  $C_{max}$  – maximum plasma concentration after the first and the fourth intravenous administration
2.  $T_{max}$  - time until  $C_{max}$  is reached
3.  $AUC_{(0-72)}$  – area under the plasma concentration curve from administration to 72 h after the first and the fourth intravenous administration.

$$AUC_{(0-72)} = \sum_{p=2}^{15} \frac{(C_p + C_{p-1}) * (t_p - t_{p-1})}{2},$$

где  $C_p$  plasma concentration at the moment  $t_p$  (hours);

$t_p \in \{ 0; 0.083; 0.167; 0.25; 0.33; 0,5; 0.75; 1; 2; 4; 8; 16; 24; 48; 72 \}; p=1, \dots, 15$

4.  $AUMC_{(0-72)}$  - the total area under the plasma concentration curve from administration to 72 h after the first and the fourth intravenous administration.

$$AUMC_{(0-72)} = \sum_{p=2}^{15} \frac{(C_p * t_p + C_{p-1} * t_{p-1}) * (t_p - t_{p-1})}{2},$$

где  $C_p$  – plasma concentration at the moment  $t_p$  (hours),

$t_p \in \{ 0; 0.083; 0.167; 0.25; 0.33; 0,5; 0.75; 1; 2; 4; 8; 16; 24; 48; 72 \}; p=1, \dots, 15$

5. Total clearance (CL) will be calculated as:

$$CL = \frac{DOSE}{AUC_{0-72}}$$

6. Mean Residence Time (MRT) will be calculated as:

$$MRT = \frac{AUMC_{0-72}}{AUC_{0-72}}$$

7. Apparent volume of distribution ( $V_d$ ) will be calculated as:

$$V_d = CL * MRT$$

8. Elimination rate constant ( $K_{el}$ ) will be calculated as:

$$k_{el} = \frac{1}{MRT}$$

9. Plasma concentration half-life ( $T_{1/2}$ ) will be calculated as:

$$T_{1/2} = \frac{\ln(2)}{k_{el}} = \ln(2) * MRT$$

10. Area under the plasma concentration curve from 0 to infinity ( $AUC_{(0-\infty)}$ ) will be calculated as:

$$AUC_{(0-\infty)} = AUC_{(0-72)} + \frac{C_{72}}{k_{el}}, \text{ где}$$

$C_{72}$ - plasma concentration of the drug during the 72 hours after the administration of the drug

11. The residual area will be calculated as:

$$\frac{AUC_{(0-\infty)} - AUC_{(0-72)}}{AUC_{(0-\infty)}}$$

Pharmacodynamics parameters

Based on determined hemoglobin level, reticulocytes counts, RBC counts, hematocrit a number of the pharmacodynamics parameters will be calculated for the study drug:

1.  $E_{max}$  – the maximum hemoglobin level (reticulocytes, RBC, hematocrit)
2.  $T_{max}$  - the time to the absolute maximum increase of hemoglobin level ( $E_{max}$ ) (reticulocytes counts, RBC, hematocrit)
3.  $AUEC_{(1-29)}$  – area under effect curve from the moment of injection to the day 29 after repeated IV injections test drug/reference drug based on the hemoglobin level (reticulocytes counts, RBC, hematocrit)

$AUEC_{(1-29)}$  will be calculated as:

CONFIDENTIAL

Version 1.0 dated 10-Oct-2016

Page 16 of 17

$$AUEC_{(1-29)} = \sum_{p=2}^{16} \frac{(C_p + C_{p-1}) * (t_p - t_{p-1})}{2},$$

где  $C_p$  hemoglobin level (reticulocytes counts, RBC, hematocrit) in the time point  $t_p$  (days);

$$t_p \in \{ 0; 1; 3; 5; 7; 8; 10; 12; 14; 15; 17; 19; 21; 22; 24; 28 \}; p=1, \dots, 16$$

4. **AC-Emax** – absolute maximum increase in the test parameter vs. baseline based on the change in the hemoglobin level (absolute reticulocyte count, erythrocytes count)

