## 3. STUDY DESIGN

### 3.1. Design

Clinical study BCD-066-3 was a double-blind controlled, randomized, parallel-group study of the pharmacokinetics, pharmacodynamics, tolerability, and safety of repeated-dose intravenous BCD-066 and Aranesp®.

The study was planned to include 62 healthy male volunteers (56 active participants and 6 back up subjects to replace dropouts). Before inclusion in the study, all potential participants are

given full information about the study. This information is presented in the Participant Information Sheet. If the potential participant gives his consent to be in the study, he has to sign the Informed Consent Form for participation in a clinical study and then undergo a 14-day screening examination to confirm that he is eligible for the study.

After passing the screening and being considered eligible for the study, subjects are centrally randomized at a 1:1 ratio to one of two treatment groups (#1 and #2).

- Subjects in Group #1 will receive IV injections of 1.0 µg/kg BCD-066 on Day 1, Day 8, Day 15, and Day 22.
- Subjects in Group #2 will receive IV injections 1 µg/kg Aranesp® on Day 1, Day 8, Day 15, and Day 22.

This is a double blind study, which means that neither the investigator nor the subject will know what drug is used in each group.

Blood samples for evaluation of darbepoetin alfa concentration will be collected 30 min, 20 min, and 10 min before the injection, immediately before the injection (not more than 5 min before drug administration), and then 5 min, 10 min, 15 min, 20 min, 30 min, 45 min, 1 h, 2 h, 4 h, 8 h, 16 h, 24 h, 48 h, and 72 h after the first and the fourth IV injection. There will be 4 blood collections before and 14 blood collections after the first and the fourth IV injection of darbepoetin alfa. The serum concentrations will be used to calculate the key PK parameters of darbepoetin alfa. Before the second and the third injection, blood samples will be collected only once. During the entire study, there will be 38 blood collections for PK evaluation.

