### **3.2. Time Points for Blood Sampling to Evaluate PK and PD**

In this study, blood samples will be collected according to the schedule to measure the concentration of darbepoetin alfa, evaluate the hemoglobin-based PD parameters, and to evaluate additional characteristics of the red blood (reticulocytes, RBC, hematocrit). The study also involves procedures to monitor the safety.

Blood samples for darbepoetin alfa concentration will be collected before and after each IV injection of the test/reference drug.

Collections will be performed as follows:

- Visit 1 (Day 1 – Day 2): 30 min, 20 min, 10 min and immediately before the first injection of darbepoetin alfa and then 5 min, 10 min, 15 min, 20 min, 30 min, 45 min, 1 h, 2 h, 4 h, 8 h, 16 h, and 24 h after the first injection.
- Visit 2 (Day 3): 48 h after the first injection.
- Visit 3 (Day 4): 72 h after the first injection.
- Visit 5 (Day 8): immediately before the second injection.
- Visit 9 (Day 15): immediately before the third injection.
- Visit 13, (Day 22 – Day 23): 30 min, 20 min, 10 min and immediately before the fourth injection of darbepoetin alfa and then 5 min, 10 min, 15 min, 20 min, 30 min, 45 min, 1 h, 2 h, 4 h, 8 h, 16 h, and 24 h after the fourth injection.
- Visit 14 (Day 24): 48 h after the fourth injection.
- Visit 15 (Day 25): 72 h after the fourth injection.

Blood samples for PD study will be collected as follows:

- Visit 1 (Day 1 – Day 2): before the injection and 24 h (one day) after the first injection.
- Visit 3 (Day 4): 72 h (3 days) after the first injection.
- Visit 4 (Day 6): 120 h (5 days) after the first injection.
- Visit 5 (Day 8): 168 h after the first injection (immediately before the second injection).

- Visit 6 (Day 9): 192 h after the first injection (24 h after the second injection).
- Visit 7 (Day 11): 240 h after the first injection (3 days after the second injection).
- Visit 8 (Day 13): 288 h after the first injection (5 days after the second injection).
- Visit 9 (Day 15): 336 h after the first injection (immediately before the third injection).
- Visit 10 (Day 16): 360 h after the first injection (one day after the third injection).
- Visit 11 (Day 18): 408 h after the first injection (3 days after the third injection).
- Visit 12 (Day 20): 432 h after the first injection (5 days after the third injection).

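### SAP 8.4 integrates the PK and hemoglobin areas at scheduled rather than actual draw times; any off-schedule sample is misplaced, with a small effect that is cheap to remove

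*SAP*

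**What the plan says.** SAP 8.4 (Multivariate Comparison) gives the operative formulas. For AUC(0-72) and AUMC(0-72), each t_p belongs to the fixed set "0; 0.083; 0.167; 0.25; 0.33; 0,5; 0.75; 1; 2; 4; 8; 16; 24; 48; 72" hours, and C_p is the "plasma concentration at the moment" t_p. For the primary PD endpoint, AUEC(1-29), t_p belongs to "0; 1; 3; 5; 7; 8; 10; 12; 14; 15; 17; 19; 21; 22; 24; 28" days from the first injection. CL, MRT, V_d, k_el, half-life, AUC(0-inf) and residual area are all derived from the two PK areas.

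The only sampling tolerance given is for the last pre-dose PK draw, "not more than 5 min before drug administration" (SAP 3.1; the protocol's Study Design has the same rule). SAP 8.3 covers missing and doubtful values, with "Missing, unused, and spurious data will not be substituted", and is silent on samples that exist but were drawn off schedule.

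Two further entries bear on the point. The protocol's PD Endpoints define the primary endpoint as "The area under the baseline-adjusted" curve, while the formula in SAP 8.4 integrates the hemoglobin level. And Visit 12 (Day 20) is scheduled at "432 h after the first injection (5 days after the third injection") in SAP 3.2 and in the protocol's Study Procedures, while the formula places it at day 19.

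**The concern.** Coded as written, the formulas put every value at its planned time, whenever the blood was drawn. Timing is most likely to slip when volunteers come back to the clinic. That applies to the 48 h and 72 h PK samples (Visits 2, 3, 14 and 15), which bound two 24-hour trapezoids, and to 12 of the 16 PD samples (Visits 3 to 12, 15 and 16).

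One misplaced late PK sample passes through the whole chain of derived parameters, and comparing PK is the first study objective. AUEC(1-29) carries the equivalence decision. Leaving the choice between planned and actual times until the data are in hand would also add analyst discretion, in a plan that already allows its list of methods to grow during analysis (SAP 8.2).

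**Working it through.** **The plan's own figure.** Inputs from SAP 6: CV = 12.92/45.4 = 28.46%, ratio 1, 28 per group, one-sided alpha 0.05. Limits are 0.80 to 1.25. On the log scale, SD = sqrt(ln(1 + 0.2846²)) = 0.279 and SE = 0.279 × sqrt(4/56) = 0.0746, with 54 degrees of freedom. Exact TOST power is 80.95%, as stated.

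**PK.** Assumptions: mono-exponential decline with C(0) = 1, half-life 20 to 70 h, 48 h and 72 h draws both 4 h late, all others on time. Each late value is multiplied by f = 2^(−4/half-life). The two points carry trapezoid weights of 24 h and 12 h, so AUC(0-72) falls by (1 − f) × (24·C48 + 12·C72).

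- Half-life 20 h: f = 0.871, so the loss is 0.129 × (24 × 0.1895 + 12 × 0.0825) = 0.717. On an area of 27.12 this is 2.6%.
- Half-life 70 h: f = 0.961, so the loss is 0.0388 × (24 × 0.6217 + 12 × 0.4902) = 0.808. On an area of 51.63 this is 1.6%.

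Carried through the formulas of SAP 8.4:

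| Half-life | AUC(0-72) | C72 | MRT and T1/2 | AUC(0-inf) | CL |
|---|---|---|---|---|---|
| 20 h | −2.6% | −12.9% | −3.9% | −3.5% | +2.7% |
| 25 h | −2.6% | −10.5% | −3.3% | −3.6% | +2.7% |
| 49 h | −2.0% | −5.5% | −1.7% | −3.0% | +2.0% |
| 70 h | −1.6% | −3.9% | −1.2% | −2.4% | +1.6% |

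If the errors are random instead (uniform, ±2 h at 24 to 72 h, ±1 h at 16 h and minutes before that; half-life 10 to 40 h), they add an SD of 0.75 to 1.8% to AUC(0-72), with a mean shift of about 0.1% or less.

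**Hemoglobin AUEC.** Assumptions: linear rise of R g/L from day 3 to day 28, and the ten return visits without an injection (Visits 3, 4, 6, 7, 8, 10, 11, 12, 15 and 16) each off by −1, 0 or +1 day with equal chance. The baseline-adjusted area is 12.5R and the slope is R/25 per day. A one-day shift at weight w therefore changes the area by w/312.5.

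- For the nine visits after day 3, the squared weights sum to 37.5 and the shift variance is 2/3, giving 25.0. At day 3 only a late draw matters: 4 × 2/9 = 0.89. The SD is sqrt(25.89)/312.5 = 1.6%.
- The extreme, all ten visits late, is 20/312.5 = 6.4%.
- If the level is integrated, the denominator becomes 12.5R + 28 × baseline. With baseline 120 to 150 g/L (inclusion criterion 4) and R assumed 15 to 20 g/L, the SD is 0.07 to 0.11% and the extreme is at most 0.44%.

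**Effect on power.** Adding 1.6% gives a CV of sqrt(28.46² + 1.6²) = 28.50% and power of 80.80%. Across three other assumed curves with draws up to 24 h off, the added SD is 1.1 to 1.9% and power stays at or above 80.7%. With 0.1% added, power is unchanged at 80.95%.

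**Visit 12.** 432/24 = 18 days, against day 19 in the formula. The day-19 point has weight 2, so a sample really drawn at 432 h would make the baseline-adjusted area 2/312.5 = 0.6% too low (0.5 to 1.0% over the other curves), in both arms alike.

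**The case against.** The strongest reply is that nothing shows the error will occur. The documents report no timing deviations. The public protocol is a synopsis, so windows or a rule for recording clock times may exist in a fuller text. If draws are on time, the error is zero. This stands: the point is about what the formula does when a draw is off schedule.

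A reader might go further and infer that the primary comparison is threatened. The figures do not support that: power moves by about a quarter of a point at most. Lateness common to both arms largely cancels in the ratio. Chance lateness in one arm of a blinded, randomized trial is random error that the confidence interval already covers, so no systematic bias between arms is expected. The PK errors are also not differences between the products, and no PK area has a stated acceptance range.

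A reader might also construct larger hemoglobin errors. Moving every sample from Day 15 onward one day late gives 15/312.5 = 4.8%, but that moves the Day 15 and Day 22 injection visits too, and the PD population is limited to subjects dosed as the protocol requires. The 1.6%, 6.4% and 4.8% figures all apply to a baseline-adjusted area. For the level that SAP 8.4 integrates, they fall to about 0.1%, 0.4% and 0.3%. The conflict between those two definitions is a separate matter and should be settled in its own right.

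**Conclusion.** The point holds as one of specification and precision. SAP 8.4 states a rule that places every sample at its planned time, nothing in the available text replaces it, and actual elapsed time is the better choice.

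The consequence is greatest for the PK parameters: roughly 2% on AUC(0-72), 1 to 4% on MRT and half-life, and 4 to 13% on the 72 h concentration when both late draws are 4 h late. For the primary hemoglobin area it is minor on either definition. These sizes rest on assumed half-lives, response curves and timing deviations. The documents do not support a conclusion that the areas do carry error, that the sample size is inadequate, or that the equivalence decision is at risk. The Visit 12 discrepancy is a contradiction in the text, whatever the draw times prove to be.

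**What to change.** In SAP 8.4:

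- Define t_p as the actual elapsed time from the relevant injection (from the first injection for AUEC), where dosing and draw times are recorded.
- If the last sample is late, interpolate to exactly 72 h, or to Day 29 (t = 28 days).
- If it is early, extrapolate by a stated rule: log-linear with the terminal slope for PK, and the last value carried to Day 29 for PD. Interpolation alone is not enough, because no PK sample follows the 72 h draw after the fourth injection and no PD sample follows Day 29. The PK slope should come from the last measured log concentrations, since the SAP's k_el is 1/MRT.
- Use planned times only where a clock time is missing, and for summary tables and mean plots.
- State the sampling windows.
- Reconcile Visit 12: 432 h in the schedules against day 19 in the AUEC formula. The same schedule line also gives Day 20 and 5 days after the third injection, which is 336 + 120 = 456 h, or day 19.

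The cost is a few sentences and minor programming. It relies on dosing and draw times being in the source records, which the documents do not confirm. Design and sample size are unaffected.
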